1 INTRODUCTION AND STUDY RATIONALE

1.1 Research Hypothesis

Treatment with nivolumab and ipilimumab with or without SBRT will improve objective response rate when compared to nivolumab alone in subjects with metastatic Merkel cell carcinoma.

1.2 Study Rationale

The proposed trial is a Phase 2 randomized, multi-institutional study of nivolumab and ipilimumab with or without SBRT in subjects with metastatic Merkel cell carcinoma. Merkel cell carcinoma (MCC) is a rare and aggressive cutaneous neuroendocrine malignancy with a propensity for distant metastasis with a 5 year survival rate of 25% in metastatic patients¹. Currently, there is no standard of care or no available treatment for this patient population. Mono- or polychemotherapy can be used in metastatic MCC, but responses are generally short-lived with poor outcome². Therefore, there is a significant need for improved therapeutic approach for metastatic MCC patients. Unfortunately, studies to define standard care have been limited by the rarity of this cancer.

1.2.1 Rationale for Nivolumab

Epidemiology suggests that MCC may benefit from immunotherapeutic approach. MCC occurs more frequently in immunocompromised patients suggesting pathogenesis of MCC involves evasion of immune surveillance³. Furthermore, approximately 80% of MCC are associated with Merkel cell polyomavirus^{4,5}, and cancers associated with viral oncogenesis may be more immunogenic. Studies on MCC have been limited by the rarity of this cancer, but immunotherapy appears a promising therapeutic modality^{6,7}.

There are a series of on-going studies to define the role of immune checkpoint inhibitors in subjects with metastatic MCC. Of particular note, PD1 blockade has emerged as a promising therapeutic modality for metastatic MCC^{6,7}.

PD-L1 status			
PD-L1 status		PD-L1 by Stage	Percent Positive
Positive	49	Stage I	41.7%
Negative	42	Stage II	50%
Percent Positive	53.8%	Stage III	55%
Percent Negative	46.2%	Stage IV	75%

Table 1. PD-L1 expression in Merkel cell carcinoma. 91 patient samples with Merkel cell carcinoma of all stages were analyzed for PD-L1 expression by immunohistochemistry. Positive PD-L1 status was defined as IHC score > 2+ in more than 5% of tumor cells.

Nivolumab has been chosen as the standard immunotherapeutic agent. This is based on prior studies correlating PD-L1 expression to therapeutic responses to Nivolumab in melanoma⁸ and because in our retrospective study of cohort of 91 patients with Merkel cell carcinoma, 53.8% of patients demonstrated PD-L1 expression, and higher stage correlated with higher percentage of patients with PD-L1 expression (**Table 1**). Similar results have been observed by other groups⁹. Indeed, a recent

interim report of phase I/II trial of metastatic treatment-naive MCC patients on Pembrolizumab reported 14% complete response rate¹⁰. Therefore, we anticipate a significant therapeutic efficacy of Nivolumab in MCC, which is being evaluated in an on-going multi-institutional clinical trial on Nivolumab alone for virus-associated cancers including MCC conducted by BMS.

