1.4.9 Rationale for Evaluation of PD-L1 as a Predictive Biomarker of Efficacy

PD-L1 is expressed by many tumor types and its expression has been noted to correlate with decreased immune system function and worse clinical prognosis. It is hypothesized that PD-L1 expression within the tumor microenvironment, either on tumor cells, macrophages or lymphocytes is a means of evading immune system detection and destruction. Still others postulate that PD-L1 expression on tumor cells is a surrogate for interferon-gamma release from neighboring activated T cells and thus portends a good prognosis for immunotherapy agents, and in particular, agents targeting the PD-1/PD-L1 axis. Preliminary data from two small retrospective analyses supports the latter hypothesis in metastatic melanoma. PD-L1 positive status was associated with improved OS, irrespective of treatment, relative to PD-L1 negative status in subjects with metastatic melanoma (n = 56)⁴³. Similarly, objective responses to nivolumab were limited to subjects defined as PD-L1 positive in a subset of subjects from study CA209003 (n = 42), which included 18 melanoma subjects⁴⁴. In both of these studies, a prototype IHC assay was used and PD-L1 positive status was defined as 5% tumor cell membrane staining or higher within a tumor tissue sample.

In our retrospective study of cohort of 91 patients with Merkel cell carcinoma, 53.8% of patients demonstrated PD-L1 expression, and higher stage correlated with higher percentage of patients with PD-L1 expression (Table 1). Similar results have been observed by other groups⁹. The clinical significance of PD-L1 expression as a prognostic and predictive marker for immunotherapy in MCC needs to be further defined, but studies from other disease sites, most prominently from melanoma suggests that PD-L1 positivity is associated with clinical response to nivolumab.

Tumor biopsy specimens from melanoma subjects treated with nivolumab or nivolumab in combination with ipilimumab across three Phase 1 metastatic melanoma studies (CA209003, CA209004 and CA209006) and one Phase I study of completely resected Stage III or Stage IV NED melanoma (CA209007) were evaluated for PD-L1 expression. Using a cutoff of 5% tumor cell membrane staining, the PD-L1 positivity rate ranged from 27% to 45%⁴⁵⁻⁴⁷ consistent with the rate previously reported by Taube et al⁴³ at 45% (24/56 subjects) in metastatic melanoma. Importantly, in

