7.5.1 Tumor Tissue Specimens

Pre-treatment tumor tissue specimens in the form of a paraffin embedded block or a minimum of 15 unstained slides will be submitted for PD-L1 IHC assessment. These biopsy samples should be from the most recent palliative surgery or biopsy. If surgical resection or biopsy are performed at one of the treatment sites, fresh tumor tissue for cell line establishment or fresh frozen tissue for tumor cell lysate will also be requested, but not mandated. Tumor specimens not used for clinical management will be utilized for research use. Approximately half of tumor tissue from biopsy or surgery will be stored as fresh frozen tissue for future IHC or preparation of tumor cell lysate. The remaining tumor will be sent directly to the PI's laboratory in order to establish cell line.

PD-L1 stained tissue sections will be assessed by a pathologist and membranous PD-L1 expression scored in tumor and immune cells if a minimum of a hundred (100) evaluable tumor cells are present. Subjects with positive, negative or indeterminate (membrane staining is obscured by high cytoplasmic staining or melanin content) IHC already has been well established at MCC tissue core for PD-L1. The cut-off for positive PD-L1 status was defined as IHC score > 2+ in more than 5% of tumor cells.

In addition, this pre-treatment tumor sample may be used to assess other putative predictive biomarkers of SBRT, nivolumab or ipilimumab efficacy and/or to better characterize the tumor-immune microenvironment post-resection. Of note, prior studies have suggest the expression of Merkel polyomavirus in tumor correlates with better responses to PD1 blockade³⁷. Therefore, Merkel polyomavirus large T antigen will be evaluated by IHC or viral load evaluated by qRT-PCR. Various other molecular markers with potential predictive value for the treatment of MCC with nivolumab, ipilimumab and other immunotherapies are currently under investigation and may be assessed in this study. These tumor tissue biomarkers include, but are not limited to PD-1, PD-L2, TILs or subpopulations of TILs and a Th1 immune mRNA expression signature. In addition, other methods of measuring tumor PD-L1 expression may also be assessed. Characterization of the tumor-immune microenvironment post-resection may involve assessment of other T cell checkpoint receptors and ligands (eg, Lag-3, Tim-3) and intratumoral immune cell subsets, including but not limited to NK cell, B-cell and T-cell lymphocytes.

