9.3.2.2 Secondary Endpoint Methods

The PFS analyses will be conducted using a two-sided log-rank test stratified by prior immunotherapy exposure in randomized subjects. The hazard ratio and corresponding two-sided 95% CI will be estimated using a Cox proportional hazards model, with treatment group as a single covariate, stratified by the above factors. PFS curves, PFS medians with 95% CIs, and PFS rates at 6, 12, 24 and 36 months with 95% CIs will be estimated using Kaplan-Meier methodology.

The OS analysis will be conducted using a two-sided log-rank test stratified by prior immunotherapy exposure at screening in randomized subjects. The hazard ratio and corresponding two-sided (1-adjusted α)% CI will be estimated using a Cox proportional hazards model, with treatment arm as a single covariate, stratified by the above factors. OS curves, OS medians with 95% CIs and OS rates at 12 and 24 months with 95% CIs will be estimated using Kaplan-Meier methodology.

The local control (LC) of irradiated lesions will be conducted using a two-sided log-rank test stratified by prior immunotherapy exposure at screening in randomized subjects. The hazard ratio and corresponding two-sided (1-adjusted α)% CI will be estimated using a Cox proportional hazards model, with treatment arm as a single covariate, stratified by the above factors. LC curves,

LC medians with 95% CIs and LC rates at 12 and 24 months with 95% CIs will be estimated using Kaplan-Meier methodology.

To evaluate PD-L1 expression as a predictive biomarker, a Cox proportional hazards model will be used to test the interaction between PD-L1 expression (positive vs negative) and treatment arm for the primary and secondary endpoint. Additionally, ORR will be analyzed within each PD-L1 expression subgroup (positive and negative) including log-rank tests and hazard ratios with corresponding confidence intervals. PFS curves and medians will be estimated using Kaplan-Meier methodology. These analyses will be descriptive and not adjusted for multiplicity.

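### PD-L1 enters the planned analyses only as positive versus negative at one cut-off; one pre-specified continuous or graded model for ORR should be added beside the binary analysis

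*Combined protocol and SAP*

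**What the plan says.** Section 7.5.1 fixes the trial's rule: "The cut-off for positive PD-L1 status was defined as IHC score > 2+ in more than 5% of tumor cells". This is the rule behind Table 1 in Section 1.2.1 ("Positive PD-L1 status was defined as IHC score > 2+ in more than 5% of tumor cells"), where "53.8% of patients demonstrated PD-L1 expression" (49 of 91 samples, all stages) and 75% of Stage IV samples were positive.

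Section 9.3.2.2 uses that status in two ways. First, "a Cox proportional hazards model will be used to test the interaction between PD-L1 expression (positive vs negative) and treatment arm". Second, "ORR will be analyzed within each PD-L1 expression subgroup (positive and negative) including log-rank tests and hazard ratios". It calls these analyses descriptive, without multiplicity adjustment. It plans no continuous or graded PD-L1 analysis and no second cut-off.

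Three other places bear on the point. Section 1.3.2 makes PD-L1 as a predictor of ORR a secondary objective. Section 9.2.2 describes the matching endpoint by level of expression, not by status. Section 7.5.1 allows other ways of measuring tumor PD-L1 but attaches no analysis to them.

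**The concern.** Splitting a graded marker in two treats every positive tumor alike and every negative tumor alike. If the chance of response climbs with expression, that variation is lost, in a sample that is already small. At the Table 1 rates, the negative group would hold about 22 of 48 patients (48 × 0.462) or about 12 of 48 (48 × 0.25).

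At stake is a named secondary objective. A real association could be missed or imprecisely estimated, and the answer would rest on one threshold, although Section 1.4.9 says the marker's meaning in Merkel cell carcinoma is still to be established.

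**Working it through.** **Inputs from the documents.** Positive share p: 49/91 = 53.8% overall and 75% in Stage IV (Table 1). Eligibility covers recurrent, unresectable or Stage IV disease, so these two values are used as a plausible bracket. Sample size: 24 per arm, 48 in total, if both arms complete the second stage (Section 9.1.1); the synopsis says about 50. The biomarker set is limited to patients with data. Test level: two-sided 0.05 (synopsis).

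**The plan's own figures.** Exact enumeration of the Simon rule (stop at 2 or fewer of 16; fail at 6 or fewer of 24) gives a per-arm pass probability of 9.8% at a 17% response rate and 90.1% at 40%. With the Beta(1,1) selection rule, overall power is 85.5%, against the stated 85%. The sample size basis is therefore sound. The documents state no power for PD-L1.

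**Information kept by the split (assumption: normal marker, linear effect on the log-odds scale).** Relative efficiency = φ(z)² / [p(1 − p)], where z is the normal quantile at the cut-off.

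- p = 0.538: z = −0.095, φ = 0.397, so 0.397² / (0.538 × 0.462) = 0.635. Loss about 37%; 48 × 0.635 ≈ 30 effective patients.
- p = 0.75: z = −0.674, φ = 0.318, so 0.318² / (0.75 × 0.25) = 0.539. Loss about 46%; 48 × 0.539 ≈ 26 effective patients.

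**Other marker shapes, still with a linear effect.**

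| Shape | Efficiency | Loss at 53.8% positive | Loss at 75% positive |
|---|---|---|---|
| Uniform | 3p(1 − p) | 25% | 44% |
| Normal | φ(z)² / [p(1 − p)] | 37% | 46% |
| Exponential | p(ln p)² / (1 − p) | 55% | 75% |

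If the true effect is a step at the cut-off, the binary variable is the correct one and the loss is zero.

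**Power for PD-L1 against ORR (main effect).** Simulated trials of 48 patients, normal marker, overall ORR 40%, score test. At an assumed odds ratio of 2.5 per SD, power is about 79% continuous, against about 60% (53.8% positive) or 46% (75% positive) binary. A run with a lower overall ORR gave 78%, 58% and 43%.

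**The reverse case.** With a step at the cut-off (assumed ORR 50% in positives, 15% in negatives), binary power is about 74% against 53% continuous at 53.8% positive, and 59% against 33% at 75% positive.

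**The test actually planned, PD-L1 by arm.** With no PD-L1 effect in Arm A and an assumed ratio of odds ratios of 3 per SD (a linear-model interaction test on response, not a Cox model), power is about 34% continuous, against 27% or 18% binary. Expected numbers per arm of 24 are about 13 positive and 11 negative, or 18 and 6.

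**The case against.** The strongest reply is that the binary analysis may be the better one. Section 1.4.9 reports that, in a subset of one nivolumab study, responses occurred only in PD-L1-positive subjects. That pattern is at least compatible with a threshold, and under a step the continuous form loses about 20 to 26 percentage points of power. A single cut-off fixed in advance also prevents shopping for cut-points. The analyses are already labelled descriptive, and the interaction is underpowered in either form. All of this stands. It rules out replacing the binary analysis, but it does not argue against adding one fixed graded model.

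Three stronger readings are tempting, and the documents do not support them.

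- A reader might infer that the plan discards 37% to 46% of the marker's information as a matter of fact. Those figures need a normal marker and a linear effect, and the documents give neither a distribution nor an effect shape.
- A reader might infer that the cut-off is too strict, or clashes with the evidence cited for it. In the studies summarised in Section 1.4.9, "PD-L1 positive status was defined as 5% tumor cell membrane staining or higher within a tumor tissue sample", with no intensity condition mentioned; the trial's rule adds one. But that is silence in a short summary of melanoma-led studies, and the trial's rule still classed 75% of Stage IV samples as positive.
- A reader might infer that the percentage is already on file. Applying the rule requires only a judgement above or below 5%. The 100-cell minimum in Section 7.5.1 is an evaluability condition and does not show that a percentage is recorded.

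**Conclusion.** The point holds as a gap in the planned analysis. Section 9.3.2.2 specifies PD-L1 only in binary form at one cut-off, and nothing graded accompanies it, although the objective is a named one and Section 9.2.2 speaks of expression level.

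The cost is conditional on the unknown shape of the relation. It is about 37% to 46% of the information under a normal marker with a log-linear effect, about 25% to 75% across the other shapes examined, and nothing under a step at the cut-off, where the binary form is better. The main-effect power loss (79% to 60% or 46%) rests on the assumed odds ratio of 2.5 per SD. It does not describe the interaction test in Section 9.3.2.2, where no choice of scale gives adequate power with 48 patients.

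Because the shape is unknown, planning both forms is the sensible position. Whether ORR should be handled by Cox and log-rank methods at all, and why Section 9.2.2 names RFS for this objective, are separate questions. Settling them would still leave the marker dichotomised.

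**What to change.** 1. Keep the binary analysis at the Section 7.5.1 cut-off.
2. In Section 7.5.1, require the percentage of PD-L1-staining tumor cells to be recorded when the slide is read, and state the staining intensity at which cells are counted.
3. In Section 9.3.2.2, add one pre-specified logistic model for ORR with that percentage as a continuous or graded covariate on one named scale (for example rank), treatment arm, and the PD-L1-by-arm term. Label it descriptive, like the other PD-L1 analyses.
4. Optionally, add a table at the Section 1.4.9 definition (membrane staining in at least 5% of tumor cells). This requires staining at any intensity to be recorded as well.

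The cost is one extra recorded value per patient and a few lines of text, with no further patients, tissue or procedures. The added model assumes a monotone, roughly linear relation on the chosen scale and loses power if the truth is a step; the retained binary analysis covers that case. Naming a single scale in advance keeps the addition from opening a choice among results.

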1.2.2 Rationale for Combining SBRT with Nivolumab

More recently, the capacity of radiation therapy to induce systemic responses via immune-activation, termed abscopal effect, has been an area of active research¹¹⁻¹⁵. Preclinical studies from our laboratory and others have demonstrated a strong synergy between radiation therapy and immunotherapy (**Fig 1**)^{11,16,17}, which has now been demonstrated in a melanoma clinical trial¹⁸.

While the abscopal effect in MCC is only anecdotal¹⁹, our preliminary data suggests its presence in MCC. We conducted a retrospective study of 300 stage I – II MCC patients treated with surgical resection alone vs. surgery and adjuvant radiation therapy at Moffitt Cancer Center. Adjuvant radiation therapy improved LRC (71.5% vs. 37.8% at 3 years, respectively; $p < 0.001$), DFS (57.0% vs. 30.2% at 3 years, respectively; $p < 0.001$) and OS (73% vs. 66%, respectively; $p = 0.02$), on both univariate and multivariate analysis (**Fig 2**)²⁰. More interestingly, there were trends for improved distant metastasis free survival (DMFS) with adjuvant radiation therapy (67% vs. 59%, respectively; $p = 0.07$) (**Fig 2**). The overall survival and DMFS benefit from radiation therapy in a disease model prone for distant metastasis suggests the abscopal effect as an underlying mechanism.

Among various immune checkpoint inhibitors, the abscopal effect of SBRT is likely to be most strongly synergistic with nivolumab. There is pre-clinical evidence that radiation therapy up-regulates PD-L1 in tumor cells (**Fig 3**) highlighting the role for PD1 axis in tolerogenic tumor microenvironment antagonizing systemic immune responses during radiation therapy. Consistently, murine studies have demonstrated that targeting PD-L1/PD1 axis results in significantly enhanced anti-tumoral immune responses induced by ionizing radiation¹⁶. Furthermore, PD-L1 expression was associated with the mechanism of resistance to combined radiation therapy and ipilimumab in melanoma²¹.

The rationale for SBRT to a total dose of 24Gy in 3 fractions as opposed to conventional radiation therapy is several fold. Preclinical studies have demonstrated that high dose per fraction appears to be most immunogenic^{22,23} leading to immune activation. At this higher dose per fraction, a more conformal treatment delivered through SBRT is necessary for safety. Moreover, by completing radiation therapy in fewer fractions, we can avoid repeated irradiation to the tumor infiltrating lymphocytes, which will render them ineffective. Also, conformal radiation therapy offered by SBRT will spare lymphoid tissues where the immune synapse occurs during priming. While definitive and adjuvant radiation therapy for MCC has traditionally involved a prolonged course of radiation therapy with wider radiation field, a recent study demonstrates that a single fraction of 8Gy radiation RT therapy offers durable palliation in MCC²⁴. Therefore, a more conformal treatment

[figure not shown]

Figure 1. Synergistic antitumor effects of combined radiation therapy and CTLA4 immunotherapy. (A) B16F10 tumor bearing mice were treated with CTLA4 mAb and/or 15Gy local radiation therapy, and tumor growth was assessed at indicated time points. * indicates $p < 0.05$ at indicated time points. (B) CD3⁺ T cells purified from spleens from mice in A were sorted, and re-stimulated ex vivo with irradiated B16F10 cells, and proliferation was measured by ³[H]-thymidine uptake.

[figure not shown]

Figure 2. Adjuvant radiation therapy impacts survival in Merkel cell carcinoma. Adjuvant radiation therapy improved (A) 3-year LRC, (C) DFS, (D) OS, which was statistically significant on both univariate and multivariate analysis. There was also a trend toward improved distant metastasis free survival (DMFS) (B) with adjuvant XRT.

delivered through SBRT is more appropriate in the metastatic setting as a modality for systemic immune activation while providing local control benefit with minimal acute and long-term toxicities.

[figure not shown]

Figure 3. Ionizing radiation upregulates PD-L1 in melanoma. B16F10 and SM1 murine melanoma cells were irradiated to 15Gy and surface expression of PD-L1 was analyzed by flow cytometry.

1.2.3 Rationale for Combining Ipilimumab with Nivolumab and SBRT

Although ipilimumab has not been tested directly in MCC following withdrawal of the clinical trial prior to accrual (NCT01913691), ipilimumab has shown efficacy in melanoma, lung cancer, prostate cancer and multiple other immunogenic cancers. Therefore, a strong clinical activity in MCC is anticipated. Furthermore, the rationale for combining ipilimumab with nivolumab has been well demonstrated by a series of Checkmate studies in different disease sites including melanoma²⁵⁻²⁷ and NSCLC²⁸. These studies demonstrated

significant improvement in objective response rate and progression free survival with the addition of ipilimumab. Notably, the abscopal effect of radiation therapy has been most extensively studied in combination with ipilimumab. Both radiation therapy and ipilimumab are thought to induce priming event for eliciting anti-tumor immune responses. Synergy of these two modalities has been demonstrated in multiple preclinical models^{15,17} as well as in the prospective clinical trial²⁹. For instance, 14% CR rate with XRT + Ipilimumab in a phase II metastatic melanoma trial is contrasted with 1.5% CR rate in the phase III trial on the Ipilimumab alone arm^{29,30}. Interestingly, PD-L1 expression has been proposed as the major mechanism of resistance to the combination of radiation therapy and ipilimumab. Therefore, there is a strong rationale to test whether ipilimumab will further potentiate the efficacy of SBRT and Nivolumab in MCC²¹.

